8 DATA COLLECTION

An electronic data capture system will be used in this trial. Data will be captured onto source data documents (Workbooks) and will be entered into the Remote Data Capture system by staff at the clinical site. Following data entry, the data will undergo quality control checks. Any discrepancies will be resolved in the database.

Following all data validation steps, the Principal Investigator, or designee, will electronically sign each eCRF prior to database lock.

CONFIDENTIAL

Synoptic Clinical Study Protocol
Version 2.0 - 05/08/2017

EudraCT Number: 2017-000380-33

9 EVALUATION OF STUDY DATA

9.1 Evaluation of Pharmacokinetic Parameters

Pharmacokinetic parameters of Y14 will include: maximum observed concentrations (C_{max}), time of occurrence of C_{max} (T_{max}), area under the plasma concentration-time curves ($AUC_{0-\infty}$, AUC_{0-t} , $AUC_{0-\tau}$), the apparent terminal rate constant (λ_z), the apparent terminal half-life ($t_{1/2}$) and the extent of accumulation in plasma (R_O). Pharmacokinetic parameters will be calculated, where appropriate, by non-compartmental analysis using WinNonlin Pro Version 5.2.1 (or higher version). Full details of the pharmacokinetic analysis, associated statistics and reporting will be documented in a separate Pharmacokinetic Analysis Plan which will be distributed to the Sponsor and Principal Investigator for approval.

9.2 Evaluation of Pharmacodynamic Measures

9.2.1 Visual Analogue Scales

Change from baseline values will be calculated using Day -1 values as baseline.

9.2.2 Energy Intake

The energy value per unit of weight will be determined for each individual component of a meal. Each component of the meal will be weighed pre and post-meal and the weight consumed will be calculated (i.e. weight pre meal - weight post meal = weight consumed). Total energy intake will be calculated from the weight of each component consumed.

9.2.3 Body Weight

Change from baseline values will be calculated using the mean of Day -1 (AM and PM) and Day 1 (predose) values as baseline.

9.2.4 Immunogenicity

Immunogenicity data will be presented as 'yes/no' based on a cut-off for binding to labelled Y14 in the immunogenicity assay (Section 7.2.5).

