3.1 Background Information for Y14

Y14 is a human peptide YY (PYY) analogue that is being evaluated by Imperial College London as a potential treatment for obesity.

It was selected from about 1500 PYY analogues that were screened for human neuropeptide Y2 receptor (Y2r) binding, mouse Y2r binding and anorectic and weight-reducing effect in rodents. The amino acid sequence of Y14 is based on human PYY₁₋₃₆, with the following features:

- Deletion of the first residue;
- Substitution of six other residues within the 35-residue peptide with the receptor active sequence of PYY being unchanged
- Composition wholly of natural L-amino acids without derivatisation or cross linking.

CONFIDENTIAL

Synoptic Clinical Study Protocol
Version 2.0 - 05/08/2017

EudraCT Number: 2017-000380-33

For further information please refer to the Investigator's Brochure (IB) [14].

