Exploratory PD evaluation will include evaluation of visual analogue scales (VAS) of nausea and satiety. Subjects in Cohort 3 onwards will undergo food intake studies on Day -1 and Day 1. The timing of the food intake study may be modified according to emerging PK data.

Blood samples for immunogenicity assays will be collected prior to the first dose (Treatment Period 1) and at the final follow-up visit for the volunteers from Cohort 1 only (as these volunteers have received multiple doses of Y14).

All subjects will return for a follow up visit 14 days (\pm 1 day) after the final dose.

Following discharge of subjects and depending on emerging PK data, the subjects (except cohort 1, dose level 1 and 2) may return to the clinical unit for further outpatient visits. The

CONFIDENTIAL

Synoptic Clinical Study Protocol
Version 2.0 - 05/08/2017

EudraCT Number: 2017-000380-33

number of additional visits per subject will not exceed six and will not extend beyond 8 weeks after each final dosing occasion. If additional outpatient visits are scheduled the final outpatient visit will be considered to be the final follow up visit where the follow-up visit assessments will be performed.

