After each inpatient stay, subjects will return to the clinical unit for outpatient visits as described in Figure 5.1,

Safety monitoring will include assessment of adverse events (AEs), physical examination, 12-lead ECGs, vital signs (blood pressure, pulse rate and body temperature) and clinical laboratory safety tests (serum biochemistry, haematology, coagulation, TSH, FT4, and urinalysis).

Blood samples for biomarker (tryptase) will be collected immediately and 12 hours after any possible allergic or anaphylactic adverse reaction. These samples will only be analysed if there is a relevant adverse reaction.

The PK evaluation will include measurement of plasma Y14 levels and associated PK parameters.

Exploratory PD evaluation will include evaluation of the following: glucose tolerance (as assessed by a standard 75 g oral glucose tolerance test before and after treatment), energy intake at mealtimes, body weight, visual analogue scales (VAS) of nausea and satiety and enteropancreatic hormones.

Blood samples for immunogenicity assays will be collected predose and at the final follow-up visit.

Subjects will attend a final follow-up visit on Day 70-73. If deemed necessary, unblinding will be performed as outlined in Section 6.9.

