7.2.5 Immunogenicity

For assessment of immunogenicity, plain tube serum samples (6 mL blood volume) will be collected prior to the first dose and at the final follow-up visit for SAD Cohort 1 and the MAD study, as subjects will be receiving multiple doses of the same peptide in these studies. Samples will be analysed using a GLP compliant and validated assay method utilising an ELISA (bridging assay format) using rabbit positive control antibodies raised against Y14.

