10.5 Pharmacodynamic Analysis

Observed values for all pharmacodynamic parameters will be listed and where appropriate, summarised with descriptive statistics.

Change-from-baseline may be calculated if appropriate.

Immunogenicity data will be presented as 'yes/no' based on a cut-off of binding to labelled Y14 in the immunogenicity assay (Section 7.2.5).

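### Immunogenicity is presented only as yes/no, with no stated role for the pre-dose sample, so a rise in a subject already positive before dosing cannot be seen

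*Combined protocol and SAP*

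**What the plan says.** Section 7.2.5 of the combined protocol and SAP provides for two serum samples per subject, which "will be collected prior to the first dose and at the final follow-up visit for SAD Cohort 1 and the MAD study". The reason given there is that these subjects receive the peptide more than once. Section 5.1.1 (Cohort 1) and section 5.1.2 (Part B) agree on the timing; for Part B, "Blood samples for immunogenicity assays will be collected predose and at the final follow-up visit". Tables 7.1 and 7.2 also count two immunogenicity samples, under the pharmacodynamic heading. The assay is a validated bridging ELISA. No cut-off value, titre step or variability figure is given.

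The evaluation rule is in section 9.2.4: "Immunogenicity data will be presented as 'yes/no' based on a cut-off for binding to labelled Y14 in the immunogenicity assay". Section 10.5 repeats it almost word for word: "Immunogenicity data will be presented as 'yes/no' based on a cut-off of binding to labelled Y14 in the immunogenicity assay". Neither section mentions the pre-dose result, an induced or boosted response, or a quantitative reading.

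Section 10.5 also has two general sentences covering all pharmacodynamic data. One says that observed values will be listed, and summarised where suitable. The other makes change from baseline optional.

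**The concern.** The sampling is a paired design, but the stated evaluation does not say how the pair is used. A yes at follow-up can arise in three ways: antibodies that appeared after dosing, binding that was there before and did not change, or binding that was there before and increased. The first and third are effects of treatment and the second is not. A yes/no entry at each visit separates the first from the other two. It cannot separate the second from the third.

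What is at stake is the description of antibody response in the first human study to give repeated doses of Y14. If a pre-dose positive subject's binding rose sharply, the planned presentation would look the same as no change.

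**Working it through.** The documents give no figure to reproduce: section 10.2 says the sample size was not statistically determined, and nothing is calculated for immunogenicity. The check is a count of who is sampled and a reading of what each pair of entries can show.

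**Subjects with paired samples, as planned**
- Cohort 1 (section 5.1.1): 4 subjects, three periods, one placebo subject per period and a different one each time. Each subject therefore has placebo at most once, and all 4 receive Y14.
- Part B (section 5.1.2): 3 × 8 = 24 subjects; 3 × 6 = 18 on Y14 and 3 × 2 = 6 on placebo.
- Paired samples: 4 + 24 = 28 subjects. Exposed to Y14: 4 + 18 = 22. Placebo only: 6, all in Part B.

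**What a pair of yes/no entries shows**

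| Pre-dose | Follow-up | Reading if both entries are compared |
|---|---|---|
| no | no | no response detected |
| no | yes | newly positive |
| yes | no | binding fell below the cut-off |
| yes | yes | unchanged, decreased but still above the cut-off, or increased: not distinguishable |

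The loss is confined to the last row, that is, to subjects positive before dosing.

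**How many subjects that could be**

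Let p be the proportion positive before dosing. The documents give no value, so the values below are assumptions. The expected number among the 22 is 22p, and the chance of at least one is 1 − (1 − p)^22.

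| Assumed p | 22p | 1 − (1 − p)^22 |
|---|---|---|
| 2% | 0.44 | 36% |
| 5% | 1.10 | 68% |
| 10% | 2.20 | 90% |

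These figures count subjects in whom a rise would be hidden if one occurred. They do not say that a rise occurs.

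**Whether placebo could stand in for the pre-dose sample**

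The chance that none of the 6 placebo subjects is positive is (1 − p)^6: 0.95^6 = 74% at 5% and 0.90^6 = 53% at 10%. Placebo would often show no background binding even where some exists. Cohort 1 has no placebo-only subject at all.

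**Comparison with neighbouring sections**

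Sections 9.2.1 and 9.2.3 define the baseline for the visual analogue scales and for body weight. Section 9.2.4 defines none. Section 9.1 defers pharmacokinetic detail to a separate analysis plan; no such plan is named for immunogenicity.

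**The case against.** A reader might infer that results are judged on the follow-up sample alone, so that background binding is counted as a drug response and the percentages above become chances of a false signal. The documents do not support this. They specify no follow-up-only rate. They say that the data are presented as yes/no, and on a plain reading both samples get an entry. A pre-dose yes beside a follow-up yes already reveals binding that preceded treatment. The false-signal reading needs someone to ignore the pre-dose entry.

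A reader might also infer that pre-existing binding is likely because Y14 is close to the human hormone. Section 3.1 describes "Substitution of six other residues within the 35-residue peptide with the receptor active sequence of PYY being unchanged", which leaves 35 − 6 = 29 residues in common. That is a fact about sequence. The documents report no pre-existing binding to Y14, to the hormone or to the earlier analogue.

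Nor do the documents treat immunogenicity as a leading result. It is absent from the objectives (section 4), the target variables (section 10.1) and the stopping rules (section 5.1.4). In Part B the second sample falls at Day 70-73, after dosing has ended.

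All of this stands, and it limits the point. The remaining defence is that the general sentences in section 10.5 might bring the raw signal into a listing. That cannot be relied on: change from baseline is optional there, and the sentence specific to immunogenicity fixes the presentation as yes/no. Change from baseline in a yes/no result would still not show a rise from a positive start.

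The lack of a stated Y14-placebo comparison is not peculiar to immunogenicity. Section 10.5 gives no treatment grouping for any pharmacodynamic variable.

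**Conclusion.** The point holds in a limited form. Sections 9.2.4 and 10.5 do not say how the pre-dose sample is used, and a yes/no result cannot show a rise in a subject who was already positive. Pre-existing binding itself would be visible from the two entries, although no rule requires them to be paired.

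The size is unknown. It depends on a rate of pre-existing binding that the documents do not give and on whether boosting happens at all. The 0.4 to 2.2 subjects among 22 rest on assumed rates of 2% to 10% and on the planned cohort sizes, without additional cohorts. The outcome is descriptive, and no sample size, error rate or dosing decision in the plan rests on it. This is a minor improvement to a stated rule.

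**What to change.** In sections 9.2.4 and 10.5:
- Name the pre-dose sample as baseline.
- Classify a follow-up result as treatment-induced (pre-dose no, follow-up yes) or treatment-boosted (pre-dose yes, with a rise in assay signal beyond a limit set in advance from the assay validation).
- List the quantitative signal at both visits beside yes/no. This also helps in reading a subject close to the cut-off, where a change from no to yes may be assay noise.
- Cross-tabulate pre-dose by follow-up status for Y14 and placebo in Part B. Show Cohort 1 separately, since all four planned subjects receive Y14 and no placebo comparison is possible there.

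The cost is a few sentences, one more listed field, and a limit for a rise agreed with the assay laboratory before results are seen. No extra samples or visits are needed. Titration of positive samples would add laboratory work and is optional.

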9.3 Evaluation of Safety

The safety evaluation will include blood pressure, pulse rate, ECG parameters, clinical laboratory tests (haematology, serum biochemistry, coagulation, urinalysis and urine microscopy). Histamine and tryptase determinations will only be performed after relevant adverse events and analysed retrospectively to inform possible mechanism of AEs.

CONFIDENTIAL

Synoptic Clinical Study Protocol
Version 2.0 - 05/08/2017

EudraCT Number: 2017-000380-33

10 STATISTICAL METHODS

10.1 Primary and Secondary Target Variables

Primary Target Variables

- Safety and tolerability as assessed by adverse events, vital signs, physical examination, clinical laboratory safety assessments, and ECG parameters.

Secondary Target Variables

- Pharmacokinetics of Y14 as measured by plasma concentrations and derived pharmacokinetic parameters.

Exploratory Target Variables

- The effects of multiple doses of Y14 on food consumption.
- The effects of multiple doses of Y14 on VAS (nausea and satiety).
- The effects of multiple doses of Y14 on body weight.
- The effects of multiple doses of Y14 on enteropancreatic hormone levels.
- The comparative analytical performance of an Imperial College radioimmunoassay versus the LC-MS/MS assay for Y14.
-

10.2 Sample Size Determination

This is a Phase I study to investigate the safety and tolerability of a novel compound, an appropriate sample size cannot be statistically determined and hence the sample size chosen was based on previous experience in Phase I studies.

10.3 Subject Population for Analyses

Safety Population

All subjects who receive study medication (Y14 or placebo) will be included in the safety population.

Pharmacokinetic Population

All subjects who receive Y14 and have data from at least 1 PK blood draw will be included in the PK population.

Pharmacodynamic Population

All subjects who receive study medication and have data from at least 1 PD blood draw or measurement, as appropriate will be included in the PD population.

CONFIDENTIAL**10.4 Pharmacokinetic Analysis**

██████████ will be responsible for the pharmacokinetic analysis. The pharmacokinetic analysis will be conducted at a Good Laboratory Practice compliant facility which operates a Quality Management System (QMS). The QMS has been designed to be compatible with the Organisation for Economic Co-operation and Development (OECD) Principles of GLP and GCP requirements. The pharmacokinetic analysis will be reported at ██████████ and the report will be included as an appendix to the clinical report. All data generated at ██████████ will be dispatched to the Sponsor and archived according to their archiving procedures.

A review of dosing information will be performed to consider excluding data in any period or on any day where a subject was judged to have received <80% or >120% of the scheduled dose of the investigational product; resulting exclusions will be documented in advance of issuing the draft report and agreed with the Sponsor. Plasma concentration data will be excluded for the affected period or day if concentrations are extremely low relative to other subjects' data; in these cases, plasma concentrations will be excluded from all or part of the profile, as appropriate.

PK parameters will be excluded from the analysis and summary statistics, where there are insufficient plasma concentration data available.

Plasma concentration data will be summarised by sampling time, dose level and Day, as appropriate; pharmacokinetic parameters (e.g. $AUC_{0-\infty}$, AUC_{0-t} , $AUC_{0-\tau}$, C_{max} , t_{max} , $t_{1/2}$ and R_o) will be summarised by dose level and Day, as appropriate.

All individual plasma and pharmacokinetic parameter estimates will be listed and summarised. Mean and individual plasma concentration versus time profiles will be illustrated using both linear-linear and logarithmic-linear scales.

Summary statistics will include number of subjects (n), arithmetic mean and standard deviation (SD). Summaries for the pharmacokinetic parameters will also display the median, minimum and maximum. In addition, the geometric mean and geometric coefficient of variation

$(CV = \sqrt{\exp(SD_{\ln}^2)} - 1 * 100$, where SD_{\ln} is the standard deviation of the natural logarithmically transformed data) will be reported for all pharmacokinetic parameters except t_{max} .

Between-subject variability will be based on geometric mean coefficients of variation (CVs).

A non-linear power model will be used to assess dose-proportionality. The proportional relationship between each parameter and dose is written as a power function:

$$y = a \times dose^b \text{ (Equation 1)}$$

where 'a' is a constant, 'b' is the proportionality constant and 'y' is the parameter of interest ($AUC_{0-\infty}$, AUC_{0-t} , $AUC_{0-\tau}$ or C_{max}). $AUC_{0-\tau}$ (after repeated dosing) $AUC_{0-\infty}$ (or AUC_{0-t} if AUC_{0-t}

CONFIDENTIAL

∞ could not be reliably estimated in all subjects) and C_{max} will be each plotted against dose. The exponent, b , will be estimated by performing a linear regression of the logged parameter on log dose. The exponent, b , is the estimated slope of the resulting regression line since taking logs of Equation (1) gives the linear relationship, $\log y = \log a + b \times \log \text{dose}$. The relationship is dose-proportional when $b = 1$. The exponents and 95 % confidence intervals (CIs), b_{lower} (b_l) and b_{upper} (b_u), are presented. There would be evidence of non dose-proportionality if this CI excludes one. The estimate of the fold increase in exposure for a doubling in dose (with 95 % CI) will also be presented. The increase in exposure expected for a doubling in dose will be calculated as 2^b (95 % CI: 2^{b_l} , 2^{b_u}).

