5.1.1 Part A (Single Ascending Dose)

Part A is a double blinded, randomised, placebo controlled, single ascending dose study (SAD). The following reflects the plan prior to execution of Part A. Approximately 28 eligible subjects will be enrolled in 5 sequential cohorts of overweight but otherwise healthy male subjects (BMI range of 25 to 38 kg/m²). No subject will be a member of more than 1 cohort.

Cohort 1 will comprise 4 subjects (3 active and 1 placebo). In cohort 1, each subject will be dosed in three treatment periods (TPs) with three ascending dose levels (proposed doses 1 mg, 4 mg, 8 mg Y14). The subjects will be randomised to either placebo or active treatment at each of these visits, i.e. different subjects will receive placebo in each TP. There will be a minimum washout period of 1 week between Day 1 of each TP. If any subject in Cohort 1 drops out between doses, they will be replaced.

Cohort 2 onwards will comprise 6 subjects (5 active and 1 placebo) for each cohort. Each volunteer in Cohort 2 onwards will only be dosed once in one TP. Proposed doses for cohorts 2-5 are 16 mg, 32 mg, 64 mg and 96 mg. All doses, and peptide concentrations are subject to change according to safety and PK review.

Up to eight additional cohorts of up to 6 subjects each (i.e. up to 48 subjects in total) may be enrolled if recommended by the Safety Committee (see Section 7.1.4) to increase scientific value of this study, e.g. to verify PK data or further characterise PD markers.

For each dose level, subjects will be randomised to receive a single dose of Y14 or matching placebo by SC injection (with fractionation if needed). A sentinel dosing strategy will be used as outlined in Table 5.1.

Table 5.1 Dosing Schedule: Part A

Cohort	Treatment Periods	Dosing Session	Number of Subjects	
			Y14	Placebo
1	1	Sentinel subjects	1	1
		Non-sentinel subjects	2	0
1	2-3	Sentinel subjects	0	0
		Non-sentinel subjects	3	1
2 onwards	1	Sentinel subjects	0	0
		Non-sentinel subjects*	20	4

*May be increased if additional groups are dosed

In Cohort 1, TP1, the first two subjects will be randomised such that 1 subject receives Y14 and 1 subject receives placebo. This sentinel pair will be dosed first and will be observed for at least 48 h before study drug is administered to the remainder of the cohort. Safety (vital

CONFIDENTIAL

Synoptic Clinical Study Protocol
Version 2.0 - 05/08/2017

EudraCT Number: 2017-000380-33

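### The dose-proportionality regression ignores that nine Part A profiles come from four men; for an assumed within-man correlation of 0.3 to 0.9 its 95% interval covers about 89 to 93%

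*Combined protocol and SAP*

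**What the plan says.** Section 10.4 sets the power model y = a × dose^b, takes logs, and states that the exponent "will be estimated by performing a linear regression of the logged parameter on log dose". It then says "The exponents and 95 % confidence intervals (CIs") are presented and adds the reading rule: "There would be evidence of non dose-proportionality if this CI excludes one". The same interval is carried over to the fold increase in exposure per doubling of dose. No subject effect or other allowance for repeated profiles is mentioned.

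Section 5.1.1 describes the data that feed this regression. "Cohort 1 will comprise 4 subjects (3 active and 1 placebo"), and "each subject will be dosed in three treatment periods (TPs) with three ascending dose levels (proposed doses 1 mg, 4 mg, 8 mg Y14"). Placebo rotates: "different subjects will receive placebo in each TP". From there on the design changes: "Cohort 2 onwards will comprise 6 subjects (5 active and 1 placebo) for each cohort", with one dose per man at 16, 32, 64 or 96 mg.

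Section 10.3 puts everyone who receives Y14 and has at least one PK draw into the PK population, so Cohort 1 is not set aside. Section 9.1 leaves full details to a separate Pharmacokinetic Analysis Plan, which is not among the documents.

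**The concern.** A plain linear regression takes all 29 profiles as independent. A Cohort 1 man with unusually high or low clearance moves two or three points in the same direction, and all of them lie at the low end of the dose range, where they pull hardest on the slope. The usual standard error does not see this and comes out too small.

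At stake is the only inferential PK analysis that the protocol describes. An interval that is too narrow produces more false statements that exposure is not proportional to dose, and it overstates how precisely the increase per doubling is known.

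**Working it through.** **Inputs from Section 5.1.1.** Cohort 1: three active profiles at each of 1, 4 and 8 mg from four men. With a different man on placebo each period, three men give two active profiles and one gives three (2 + 2 + 2 + 3 = 9). Cohorts 2 to 5: 4 × 5 = 20 men with one profile each. Total: 29 profiles from 24 men.

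**Assumption.** The correlation ρ between log-scale profiles of the same man is not in the documents; 0.3 to 0.9 is used. Interval widths also assume a log-scale SD of 0.4; coverage does not depend on that value.

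**Step 1: leverage.** With x = ln(dose), the mean of x is 2.938 and the sum of squares Sxx is 57.54. The 1, 4 and 8 mg profiles contribute 25.90 + 7.22 + 2.21 = 35.33. So 61% of the information on the slope rests on 31% of the profiles (9/29).

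**Step 2: true variance of the slope.** For ordinary regression,

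Var(b) = (σ²/Sxx) × (1 + ρC/Sxx),

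where C sums the products of centred doses over ordered pairs of profiles from the same man. The centred values at 1, 4 and 8 mg are −2.938, −1.552 and −0.859. Each pair of doses is shared by two men, so

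C = 2 × 2 × (2.938×1.552 + 2.938×0.859 + 1.552×0.859) = 33.66, and C/Sxx = 0.585.

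**Step 3: variance that the regression reports.** There are 12 ordered within-man pairs (three men × 2, plus one man × 6). The residual mean square therefore has expectation σ²[1 − ρ(12/29 + 0.585)/27] = σ²(1 − 0.037ρ).

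**Step 4: ratio and coverage.** The ratio of true to reported variance is (1 + 0.585ρ)/(1 − 0.037ρ). At ρ = 0.5 this is 1.2925/0.9815 = 1.32, so the reported standard error is 1 − 1/√1.32 = 13% too small. Coverage of the 95% interval on 27 degrees of freedom was simulated with 400,000 data sets per value of ρ; repeat runs agreed within 0.3 percentage points. With ρ = 0 the plan's nominal 95% is reproduced.

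| ρ | True/reported variance | SE understated by | Coverage | False-claim rate |
|---|---|---|---|---|
| 0 | 1.00 | 0% | 95.0% | 5.0% |
| 0.3 | 1.19 | 8% | 93.0% | 7.0% |
| 0.5 | 1.32 | 13% | 91.4% | 8.6% |
| 0.7 | 1.45 | 17% | 89.9% | 10.1% |
| 0.8 | 1.51 | 19% | 89.3% | 10.7% |
| 0.9 | 1.58 | 20% | 88.5% | 11.5% |

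**Step 5: does a mixed model repair it?** A random-intercept REML fit with a plug-in interval does not. With 27 degrees of freedom it covered about 93, 91, 90 and 89% at ρ = 0.3, 0.5, 0.7 and 0.9. Cutting the degrees of freedom to 10 without correcting the standard error still gave only 94 down to 91%. With the Kenward-Roger correction, coverage was 94 to 95% throughout.

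**The case against.** The strongest objection is that Section 9.1 defers the detail to a plan that we cannot see. Section 10.4 never says least squares or states an error structure, so independence is read from silence. It is true that the unseen plan may contain a subject effect. But Section 10.4 already fixes the model equation, the estimator, the interval and the reading rule, and an unqualified linear regression means ordinary regression to most analysts. A plan that followed the protocol would inherit the problem.

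Second, the size depends on a correlation that nobody has stated, and on all nine low-dose profiles being usable. Section 10.4 drops parameters with too few concentrations, 1 mg is the lowest dose, and Table 7.1 lists up to 17 PK samples for Cohort 1 despite its three periods. Without the 1 mg profiles, coverage is about 94% (ρ = 0.3) to 92% (ρ = 0.9): a smaller shortfall, still present. If only 8 mg survived, the clustering would vanish. Replacing a Cohort 1 man would weaken it. Extra cohorts at 16 to 96 mg leave coverage at about 89 to 91% for ρ of 0.5 to 0.7; eight extra cohorts all at 8 mg would bring it to 93 to 94%.

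Third, the stakes are limited. PK is a secondary objective, and escalation under Sections 5.1.1 and 5.1.4 rests on safety, tolerability and exposure review, not on this interval. That stands, and it limits the severity. It does not make the interval correct.

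A gain in precision is not a general argument for the change: with the correlation known, the slope variance would fall by only 4% at ρ = 0.3 and 11% at 0.5. The case for the change is valid coverage.

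**Conclusion.** The concern holds for the protocol as written. For the planned five cohorts with complete data, the nominal 95% interval for the Part A exponent covers about 93% at a within-man correlation of 0.3 and 88.5% at 0.9. The false-claim rate is 7.0 to 11.5% instead of 5%. The correlation is assumed, but coverage was below 95% at every positive value tried.

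The figures apply to the single-dose regressions of AUC and Cmax. They do not apply to the Part B AUC over the dosing interval, provided that each man contributes one profile there. The point should be corrected, but no dosing decision or primary objective rests on it.

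**What to change.** In Section 10.4 and the Pharmacokinetic Analysis Plan, specify for Part A: log y = log a + b × log dose + random subject intercept + residual, fitted by REML, with Kenward-Roger standard errors and degrees of freedom for the interval on b and for the derived fold increase per doubling. State that a plug-in Wald interval will not be used. Keep the ordinary regression as a sensitivity analysis. A further simple check uses one profile per Cohort 1 man, which restores independence.

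The cost is one sentence in each document and no new data. At a log SD of 0.4 the median interval width for b rises from 0.21 to about 0.23 to 0.25 for correlations of 0.3 to 0.8.
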